6.2.1. Preparation and Dispensing

Within this protocol, preparation refers to the investigator site activities performed to make the investigational product ready for administration or dispensing to the participant by qualified staff. Dispensing is defined as the provision of investigational product, concomitant treatments, and accompanying information by qualified staff member(s) to a healthcare provider or participant in accordance with this protocol. Local health authority regulations or investigator site guidelines may use alternative terms for these activities.

See the IP Manual for instructions on how to prepare and blind the investigational product for administration.

PF-06755347 and placebo should be prepared by an appropriately qualified unblinded site personnel (ie, pharmacist) according to the IP manual and dispensed by an appropriately qualified and experienced member of the study staff (eg, physician, nurse, physician's assistant, nurse practitioner, pharmacy assistant/technician, or pharmacist) as allowed by local, state, and institutional guidance. Dose preparation must be performed with locally accepted sterile handling technique and the investigational product will be administered in blinded fashion to the participant.

PF-06755347 and placebo vials are single use.

All dosing and administration calculations and dose preparation must be performed and checked by one qualified clinical site personnel and verified by a qualified and experienced second clinical site personnel (eg, physician, nurse, physician's assistant, nurse practitioner, pharmacy assistant/technician, or pharmacist). The site will take all necessary precautions to maintain the investigator and other site personnel blind.

6.3. Measures to minimize bias: Randomization and blinding

An Interactive Response Technology (IRT) system will be programmed with blind-breaking instructions. Refer to subsections [6.3.1 Allocation to Investigational Product](#) and [6.3.2 Breaking the Blind](#) for further details.

6.3.1. Allocation to Investigational Product

Allocation of participants to treatment groups will proceed through the use of an interactive response technology (IRT) system (interactive Web-based response [IWR]). The site personnel (study coordinator or specified designee) will be required to enter or select information including but not limited to the user's identification (ID) and password, the protocol number, and the participant number. The site personnel will then be provided with a

treatment assignment and randomization number, when investigational product is being supplied via the IRT system. The IRT system will provide a confirmation report containing the participant number, randomization number, and treatment assignment.. The confirmation report must be stored in the site's files.

Investigational product will be dispensed at Day 1 inpatient visit.

The study-specific IRT reference manual and IP manual will provide the contact information and further details on the use of the IRT system.

6.3.2. Breaking the Blind (for HP cohorts only)

At the initiation of the study, the investigator site will be instructed on the method for breaking the blind. The method will be an electronic process. The IRT will be programmed with blind-breaking instructions. In case of an emergency, the investigator has the sole responsibility for determining if unblinding of a participant's treatment assignment is warranted. Participant safety must always be the first consideration in making such a determination.

If the investigator decides that unblinding is warranted in the interest of the safety of a participant, the investigator should make every effort to contact the Sponsor prior to unblinding a participant's treatment assignment unless this could delay further management of the participant. However, discussion with the Sponsor in advance of unblinding is not required. If a participant's treatment assignment is unblinded, the Sponsor must be notified within 24 hours after breaking the blind.

When the blinding code is broken, the reason must be fully documented and entered on the data collection tool (DCT).

Blood specimens will be obtained from all participants for PK analysis to maintain the study blind at the investigator site. The investigator site staff and blinded study monitor, if assigned, will be blinded to IP. A designated limited number of Sponsor colleagues within the study team will be unblinded to participant treatments in order to permit real-time interpretation of the safety and PK data and provide information necessary to potentially alter the dose-escalation sequence (see [Section 9.9](#)). Specimens from participants randomized to placebo will not be routinely analyzed. To minimize the potential for bias, treatment randomization information will be kept confidential by Pfizer unblinded personnel and will not be released to the blinded investigator or blinded investigator site personnel until the study database has been locked or the investigator requests unblinding for safety reasons.

6.4. Study Intervention Compliance

The site will complete the required dosage Preparation Record located in the IP manual. The use of the Preparation Record is preferred, but it does not preclude the use of an existing appropriate clinical site documentation system. The existing clinical site's documentation system should capture all pertinent/required information on the preparation and administration of the dose. This may be used in place of the Preparation Record after approval from the Sponsor and/or designee.

6.5. Concomitant Therapy

Healthy participants will abstain from all concomitant therapies except those required for the treatment of adverse events.

Participants with ITP will be permitted to continue any medications that they routinely receive for treatment of ITP or any other co-existing medical conditions, so long as their use does not violate any inclusion or exclusion criteria. They will also be permitted to receive concomitant therapies required for the treatment of adverse events.

Acetaminophen/paracetamol, nonsteroidal anti-inflammatory drugs (for HPs only) and diphenhydramine are permitted to manage adverse events and infusion or injection related reactions.

Limited use of nonprescription treatments that are not believed to affect participant safety or the overall results of the study may be permitted on a case-by-case basis following approval by the Sponsor.

All concomitant treatments taken during the study must be recorded with indication, daily dose, and start and stop dates of administration. All participants will be questioned about concomitant treatment at each clinic visit.

Treatments taken within 56 days before the first dose of investigational product will be documented as a prior treatment. Treatments taken after the first dose of investigational product will be documented as concomitant treatments.

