 27. **ANY** of the following abnormalities in clinical laboratory tests at screening or on admission, as assessed by the study-specific laboratory and confirmed by a single repeat tests, if deemed necessary:
 - AST or ALT ≥ 1.5 x upper limit of normal); If currently taking eltrombopag, AST or ALT $> 3 \times$ ULN;
 - Total bilirubin ≥ 1.25 x upper limit of normal); If currently taking eltrombopag, total bilirubin level $> 1.5 \times$ ULN (Participants with a history of Gilberts syndrome may have direct bilirubin measured and would be eligible for this study provided the direct bilirubin level is \leq ULN);
 - Serum creatinine > 1.5 x ULN;
 - eGFR < 60 ml/min/1.73m² by CKD-EPI Formula.
 28. Participants who are investigator site staff members directly involved in the conduct of the study and their family members, site staff members otherwise supervised by the investigator, or participants who are Pfizer employees (including their family members) directly involved in the conduct of the study.

29. Other medical or psychiatric condition including recent (within the past year) or active suicidal ideation/behavior or laboratory abnormality that may increase the risk of study participation or, in the investigator's judgment, make the participant inappropriate for the study.

30. Participation in a previous cohort in the current study.

Prior/Concurrent Therapy for ITP:

31. ≤ 28 days prior to PF-06755347 dosing:

- Treatment with IVIg or an anti-Rh D antigen agent (eg, WinRho[®]).
- Treatment with high-dose pulse corticosteroid therapy (eg, dexamethasone 40mg/day for 4 days or methylprednisolone 30 mg/kg/day for 3 days).
- Other Anti-inflammatory Drugs, including NSAIDs for Cox-1 and Cox-2 (eg, Ibuprofen, naproxen, aspirin, diclofenac) or anti-IL-6 agents tocilizumab or siltuximab.

32. Within 3 months prior to PF-06755347 dosing:

- Treatment with cytotoxic agents (eg, cyclophosphamide, vincristine).
- Plasmapheresis.

33. Within 6 months prior to PF-06755347 dosing:

- Treatment with rituximab (or any other anti-CD20 agent).

Concomitant Therapy:

34. If receiving corticosteroids, the dose must be < 1 mg/kg prednisone per day or equivalent, must have been stable or decreasing for ≥ 28 days prior to PF-06755347 dosing and must be expected to remain stable or to decrease for the duration of the study.

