6.1.1.2. Guideline on Subcutaneous Injection

For participants receiving a SC injection, the number of injections will be recorded. Time 0 for the SC injection will be the time of the first injection. The preferred body location for the SC injection is the abdomen but the 5 cm area around the navel should be avoided. If abdominal injections are not possible, arm or thigh locations may also be used. If an arm is used for the SC injection, the opposite arm should be used for the PK blood sample collections. For doses that require more than one injection, individual injections should be administered approximately 3 cm away from the site of the previous injection (ie, the abdomen, same arm or thigh). Avoid umbilicus area and skin with tattoos and scarring. The maximum volume for an individual injection is 1.5 ml. Since the drug product concentration is 50 mg/mL, the maximum number of injections will be approximately 4. At SC doses that require greater than the maximum number of injections, a SC infusion will be used.

If a participant experiences an infusion or injection site reaction during the administration period, then treatment administration should be paused for that participant and supportive care should be provided according to the Investigator's standard practice (eg, treatment with an antihistamine). Treatment administration may resume at the discretion of the Investigator if there are no systemic symptoms and if the reaction resolves.

Consult the IP Manual for detailed instructions regarding study drug preparation, stability and administration. Per the drug stopping rules ([Section 6.6](#) and [Section 6.7](#)), dosing will be paused for the entire cohort, for any serious adverse event (SAE) that occurs in a participant receiving active treatment until causality is fully assessed by the PI and Sponsor.

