6.8. Infusion or Injection Site Reactions (ISR)

ISR is a type of hypersensitivity reaction that may be immediate, although it usually appears within 24-48 hrs after injection. ISR, by definition, includes the following: erythema, induration ecchymosis, pain and pruritus at the infusion or injection site.

Infusion or injection-related reactions will be assessed and managed based on the CTCAE severity scale for infusion reactions (see [Appendix 11](#)).

- Grade 1 reaction (Mild): Participant will be monitored closely at bedside while infusion or injection continues. For IV dosing, the PI may slow the infusion rate, based on medical judgement.
- Grade 2 (Moderate): Infusion may be paused, and symptomatic treatment (such as antihistamine, acetaminophen or nonsteroidal anti-inflammatory drugs (NSAIDs)) may be administered. For IV dosing, if the infusion is paused, once symptoms subside, infusion may be restarted at a 50% reduction in infusion rate. Infusion rate may be increased after 30 minutes if participant is stable.
- Grade 3 (Severe) or 4 (life-threatening): For IV dosing, the infusion will be stopped promptly. Participant will be followed until symptoms resolve, and no further follow-up regarding the AEs is needed in the opinion of the PI.
- For IV dosing, acute infusion reactions of mild-moderate severity (Grade 1 or Grade 2) which fully resolve following dose interruption and/or the administration of antihistamines/antipyretics with subsequent resumption and safe completion of dosing will not be considered dose limiting.

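### Section 6.8 lists NSAIDs for Grade 2 injection reactions without a population limit, while Section 6.5 allows them in healthy participants only

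*Protocol*

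**What the plan says.** Protocol Section 6.5 (Concomitant Therapy) sets the general rule by population. For participants with ITP it first gives a broad allowance: "They will also be permitted to receive concomitant therapies required for the treatment of adverse events". It then turns to named drugs and says that "nonsteroidal anti-inflammatory drugs (for HPs only) and diphenhydramine are permitted to manage adverse events and infusion or injection related reactions". Acetaminophen/paracetamol is in the same list, without a population limit.

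Protocol Section 6.8 (Infusion or Injection Site Reactions) tells the site how to handle a reaction by grade. Its lead-in reads "Infusion or injection-related reactions will be assessed and managed based on the CTCAE severity scale for infusion reactions". For Grade 2 it says that "symptomatic treatment (such as antihistamine, acetaminophen or nonsteroidal anti-inflammatory drugs (NSAIDs)) may be administered". That bullet does not separate healthy participants from participants with ITP and does not refer to Section 6.5.

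Protocol Section 5.4, criterion 31, excludes participants with ITP who took certain drugs in the 28 days before dosing, among them "Other Anti-inflammatory Drugs, including NSAIDs for Cox-1 and Cox-2".

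**The concern.** Two current instructions cover the same drug class for the same event and differ on who may receive it. Section 6.8 is the section a site would open when a reaction occurs, and it is the one that lacks the restriction.

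The limit in 6.5 is the sponsor's own. The documents do not explain it, but criterion 31 is consistent with it, and Section 2.3 names procedure-related bleeding and bruising from SC injection as a risk in ITP. A bleeding or bruising event of Grade 2 or higher (Grade 3 for metrorrhagia) pauses ITP dosing under Section 6.6, and Section 10.3.3 requires concomitant therapy to be weighed when causality is assessed. An NSAID given on the strength of 6.8 would be a treatment that 6.5 does not permit in ITP, and it could cloud that assessment.

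**Working it through.** No figure is being tested, so the check sets the passages side by side.

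**1. Same drug class, same use.** Section 6.5 covers adverse events and infusion or injection reactions. The Grade 2 bullet of 6.8 covers symptomatic treatment of infusion or injection reactions. The uses overlap, and only 6.5 carries the healthy-participant limit.

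**2. Does the 6.8 bullet reach participants with ITP?** They receive PF-06755347 by SC injection (Sections 1.1 and 4.1).
- The title and lead-in of 6.8 include injections.
- The Grade 1 bullet does too: "Participant will be monitored closely at bedside while infusion or injection continues".
- Within 6.8, content meant only for IV dosing is marked as such. In the Grade 2 bullet that marker comes after the NSAID sentence, where the text turns to restarting the infusion. The NSAID sentence itself is unmarked.
- Section 2.1 states that IV dosing has ended, so for new participants 6.8 now operates for SC dosing only.

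**3. Does any other text restore the limit?**
- *Section 6.5, general ITP allowance.* It does not name NSAIDs. The later sentence that does name them limits them to healthy participants. If the general allowance overrode it, the limit would have no meaning.
- *Section 6.1.1.2.* Its guidance applies "If a participant experiences an infusion or injection site reaction during the administration period" and gives an antihistamine as its example. Section 6.8 says that a reaction may be immediate, "although it usually appears within 24-48 hrs after injection", so most reactions would fall outside that guidance.
- *Section 6.5.1.1 and Appendix 10.* The rescue list for cytokine release syndrome (CRS) includes oral NSAIDs with no population limit. The fever guidance in Appendix 10 makes them a second option unless contraindicated. Neither carries the limit into 6.8.

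**4. Who would be treating?** The usual onset of 24-48 hours after injection is Day 2 to Day 3. Confinement runs through Day 8 (168 hours), so the usual onset falls while site staff are treating under the protocol.

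**5. How many participants?** Table 4 plans 3-6 in each ITP cohort. The minimum is 3 + 3 = 6 and the maximum is 6 + 6 = 12, which matches the combined maximum of 12 in Section 4.1. Table 4 marks both cohorts ND (not done).

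**The case against.** The strongest reply is that the two sections can be followed together. Section 6.8 gives examples and says they may be used; it never requires an NSAID. Section 6.5 is the specific rule on permitted drugs and divides this use by population. Staff who obey both would give a participant with ITP an antihistamine or acetaminophen. This stands as a sensible reading and keeps the point minor. But no text says that 6.5 governs, and a reader of 6.8 alone has no cue to look there.

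A second reply is that the Grade 2 bullet opens with pausing an infusion, and that Appendix 11, the scale it applies, grades infusion-related reactions. ITP doses are 25, 50 or 100 mg. At 50 mg/mL the largest is 100 / 50 = 2 mL, or two injections at a maximum of 1.5 mL each, so no SC infusion is expected. The bullet might therefore be meant for infusions, or only for reactions during dosing, which would leave later reactions to 6.5. That reading is possible, but it sits badly with the title and lead-in of 6.8 and with its habit of marking IV-only content.

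It is also fair that criterion 31 is a pre-dose washout and that the documents give no reason for the limit in 6.5. The conflict does not depend on the reason.

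**Conclusion.** The concern holds as a minor conflict in a safety instruction that is wrong as written. Section 6.8 leaves open, for SC-dosed participants with ITP, a treatment that Section 6.5 reserves for healthy participants, and nothing in the protocol resolves the difference.

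The scope is 6 to 12 participants if both ITP cohorts are run as planned. How often the conflict would matter cannot be estimated, because the documents give no rate of Grade 2 injection reactions or of NSAID use. The conclusion rests on reading the unmarked NSAID sentence in 6.8 as applying to injections, which the title, lead-in and Grade 1 bullet support. No endpoint, analysis or sample size is affected.

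**What to change.** In the Grade 2 bullet of Section 6.8, insert *(HPs only; see Section 6.5)* after NSAIDs.

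Optionally, in the same amendment, add a cross-reference to 6.5 in the CRS rescue list (Section 6.5.1.1) and the Appendix 10 fever guidance. If the sponsor does intend NSAIDs to be available for CRS in participants with ITP, state that exception in 6.5.

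The cost is one short insertion in the next amendment. Because Table 4 shows neither ITP cohort as dosed, a correction made at this version could cover every ITP participant.

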6.5.1. Rescue Medication

6.5.1.1. Rescue Therapy for CRS

Rescue therapy for CRS should be immediately available including oral paracetamol, oral NSAIDs, IV normal saline, IV corticosteroids, oxygen.

An ICU should be available for additional support and administration of vasopressors if appropriate. The availability of anti-IL-6 agents is optional.

See [Section 10.10](#) for further guidance.

6.5.1.2. Rescue Therapy for Bleeding Events in ITP Participants

Rescue therapy for bleeding events in ITP participants should be carried out in accordance with each country's/site's standard procedures and practices.¹⁹

6.6. Dose Progression

The participants within each cohort will be dosed using a sequential dosing scheme. For all cohorts, a single participant will be dosed at a given time, followed by a minimum of 72-hour (for IV) and 96-hours (for SC) safety monitoring period. In total there will be a minimum of 96 hours between each IV participant dosed and 120 hours for each SC participant dosed.

The following rules will be applied when considering dosing of the next participant in the cohort.

Sequential dosing may **proceed** only if no adverse events are reported OR all of the following criteria are met:

1. Any pro-inflammatory events are < Grade 2 Per CTCAE criteria in [Appendix 9](#).
2. All other adverse events are deemed mild or moderate in severity, regardless of relatedness.
3. Any laboratory, ECG or vital sign changes are considered not clinically significant.
4. No other pause or stop criteria are met.
5. For participants with ITP, in addition to the above criteria, no participant has greater than a 30% decrease in platelet count – defined from the immediate pre-dosing platelet count to the lowest postdosing platelet count. Dose progression will be independent of dose progression from HP cohorts at higher dose levels.

Sequential dosing should be **paused** if any criterion below is met in a participant receiving active drug:

1. Grade 2 (Objective) pro-inflammatory event (vomiting, diarrhea, hypotension or hypoxia) (see [Appendix 9](#)).
2. Adverse event which is considered to be severe (Grade 3 or higher) AND is deemed related to study intervention.
3. A moderate event (Grade 2) AND is deemed related to study intervention not otherwise identified as a proinflammatory event or AE of special interest, that in the opinion of the PI and Sponsor are of concern and warrant further investigation before additional dosing.
4. For participants with ITP, platelet count of <30 x 10⁹/L AND a decrease from baseline ≥30%, or a platelet count decrease from baseline of ≥50%, defined from the immediate pre-dosing platelet count to the lowest post-dosing platelet count, or a bleeding or bruising-related AE CTCAE 4.03 Grade 2 or higher (except metrorrhagia Grade 3 or higher).

Sequential dosing should be **stopped** at the current dose level if any criterion below is met in participant receiving active drug:

1. Grade 3 or greater pro-inflammatory event.
2. Serious adverse event that is deemed related to study intervention.

3. A single occurrence of confirmed drug induced liver injury (see [Appendix 6](#)) or confirmed drug induced kidney injury (see [Section 7.1](#)) will be reported as a serious adverse event, and therefore, will be considered dose limiting.

In the event of a dose **pause**, all available safety, PK (if available), cytokine, and complement data for the participants will be reviewed by the dose escalation subteam. The subteam should determine whether clinical symptoms associated with the pause criteria have resolved and determine whether IL-6 has returned to near baseline levels ie that the event is reversible. IL-6 has been selected as the surrogate marker for decision making purposes as it appears to be the most sensitive cytokine pathways from the non-human primate and human in vitro data. However, TNF- α , IFN- γ cytokine and complement data will be available at the time of review. If the dose escalation subteam determines that dosing may resume, a plan that mitigates risks to participants with the resumption of dosing may be implemented. Such a plan could include a revision of inclusion/exclusion criteria, repeating or reducing the dose, reducing infusion/dosing rate or adding appropriate safety monitoring or prophylactic treatment. This mitigation plan may need to be discussed with the Institutional Review Board (IRB) or Regulatory Authority as appropriate. The ultimate decision to continue dosing of study participants rests with the PI. Sponsor dose escalation subteam cannot overrule PI decision/clinical judgement.

If the decision is to **stop** dose progression this will also stop any further dose escalation.

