8.2.4. Clinical Safety Laboratory Assessments

See [Appendix 2](#) for the list of clinical safety laboratory tests to be performed and the [SoA](#) for the timing and frequency. All protocol-required laboratory assessments, as defined in [Appendix 2](#), must be conducted in accordance with the laboratory manual and the [SoA](#). Unscheduled clinical laboratory measurements may be obtained at any time during the study to assess any perceived safety issues.

The investigator must review the laboratory report, document this review, and record any clinically relevant changes occurring during the study in the AE section of the CRF. Clinically significant abnormal laboratory findings are those which are not associated with the underlying disease, unless judged by the investigator to be more severe than expected for the participant's condition.

All laboratory tests with values considered clinically significantly abnormal during participation in the study after the last dose of study intervention should be repeated until the values return to normal or baseline or are no longer considered clinically significant by the investigator or medical monitor.

If such values do not return to normal/baseline within a period of time judged reasonable by the investigator, the etiology should be identified and the Sponsor notified.

See [Appendix 6](#) for suggested actions and follow-up assessments in the event of potential drug-induced liver injury.

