10.3.1. Definition of AE

AE Definition

• An AE is any untoward medical occurrence in a patient or clinical study participant, temporally associated with the use of study intervention, whether or not considered related to the study intervention.• NOTE: An AE can therefore be any unfavorable and unintended sign (including an abnormal laboratory finding), symptom, or disease (new or exacerbated) temporally associated with the use of study intervention.

AE Definition

• An AE is any untoward medical occurrence in a patient or clinical study participant, temporally associated with the use of study intervention, whether or not considered related to the study intervention.• NOTE: An AE can therefore be any unfavorable and unintended sign (including an abnormal laboratory finding), symptom, or disease (new or exacerbated) temporally associated with the use of study intervention.

Events Meeting the AE Definition

• Any abnormal laboratory test results (hematology, clinical chemistry, or urinalysis) or other safety assessments (eg, ECG, radiological scans, vital sign measurements), including those that worsen from baseline, considered clinically significant in the medical and scientific judgment of the investigator (ie, not related to progression of underlying disease).• Exacerbation of a chronic or intermittent preexisting condition including either an increase in frequency and/or intensity of the condition.• New conditions detected or diagnosed after study intervention administration even though it may have been present before the start of the study.• Signs, symptoms, or the clinical sequelae of a suspected drug-drug interaction.• Signs, symptoms, or the clinical sequelae of a suspected overdose of either study intervention or a concomitant medication. Overdose per se will not be reported as

an AE/SAE unless it is an intentional overdose taken with possible suicidal/self harming intent. Such overdoses should be reported regardless of sequelae.

Events Meeting the AE Definition

- Any abnormal laboratory test results (hematology, clinical chemistry, or urinalysis) or other safety assessments (eg, ECG, radiological scans, vital sign measurements), including those that worsen from baseline, considered clinically significant in the medical and scientific judgment of the investigator (ie, not related to progression of underlying disease).

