- Exacerbation of a chronic or intermittent preexisting condition including either an increase in frequency and/or intensity of the condition.
- New conditions detected or diagnosed after study intervention administration even though it may have been present before the start of the study.
- Signs, symptoms, or the clinical sequelae of a suspected drug-drug interaction.
- Signs, symptoms, or the clinical sequelae of a suspected overdose of either study intervention or a concomitant medication. Overdose per se will not be reported as an AE/SAE unless it is an intentional overdose taken with possible suicidal/self-harming intent. Such overdoses should be reported regardless of sequelae.

Events NOT Meeting the AE Definition

- Any clinically significant abnormal laboratory findings or other abnormal safety assessments which are associated with the underlying disease, unless judged by the investigator to be more severe than expected for the participant's condition.
- The disease/disorder being studied or expected progression, signs, or symptoms of the disease/disorder being studied, unless more severe than expected for the participant's condition.
- Medical or surgical procedure (eg, endoscopy, appendectomy): the condition that leads to the procedure is the AE.
- Situations in which an untoward medical occurrence did not occur (social and/or convenience admission to a hospital).
- Anticipated day-to-day fluctuations of preexisting disease(s) or condition(s) present or detected at the start of the study that do not worsen.

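### Read literally, the no-AE alternative in Protocol Section 6.6 bypasses the 30% platelet limit for ITP participants; Section 6.6 also cites a table that does not grade hypotension or hypoxia

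*Protocol*

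**What the plan says.** Section 6.6 has three lists: when sequential dosing may proceed, when it is paused, and when it is stopped.

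**Proceed.** Dosing may go on "only if no adverse events are reported OR all of the following criteria are met". Five criteria follow. Criterion 3 asks that laboratory, ECG and vital-sign changes not be clinically significant. Criterion 4 asks that no other pause or stop criterion be met. Criterion 5 reads "For participants with ITP, in addition to the above criteria, no participant has greater than a 30% decrease in platelet count", measured from the immediate pre-dose count to the lowest post-dose count.

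**Pause.** For ITP, criterion 4 of this list is a count below 30 × 10⁹/L with a fall of at least 30%, "or a platelet count decrease from baseline of ≥50" percent, or a bleeding or bruising AE of Grade 2 or higher (Grade 3 for metrorrhagia). It does not depend on any other AE having been recorded.

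**What counts as an AE.** Appendix 3 (10.3.1) includes abnormal results, "including those that worsen from baseline, considered clinically significant in the medical and scientific judgment of the investigator". It also includes this: "Exacerbation of a chronic or intermittent preexisting condition including either an increase in frequency and/or intensity of the condition". Among the events that are not AEs it lists "Any clinically significant abnormal laboratory findings or other abnormal safety assessments which are associated with the underlying disease". That exclusion has one limit, which rests on the investigator's view of what the disease would produce anyway: it holds "unless judged by the investigator to be more severe than expected". Section 8.2.4 draws the same line: "Clinically significant abnormal laboratory findings are those which are not associated with the underlying disease", with the same exception.

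**Hypotension and hypoxia.** Pause criterion 1 names both as Grade 2 pro-inflammatory events and refers to Appendix 9. Proceed criterion 1 also points there. Appendix 9 has rows for vomiting and diarrhea only.

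**The concern.** Criterion 5 reads as if meant for every ITP participant, yet it sits inside the second of two alternatives. When no AE is reported the first alternative is met and criterion 5 is never consulted. Low platelets are the disease under study, so the AE definition leaves room for a post-dose fall to be attributed to ITP and not recorded. Identical platelet data could then permit or bar the next dose depending on whether some unrelated mild event was written down.

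The rule governs exposure of the next participant in a first-in-human study. Section 2.3 says high-dose IV administration may transiently lower platelets, which gives the limit a purpose.

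The second point is smaller. If the cited table has no grade for hypotension or hypoxia, it can be unclear whether such an event pauses a cohort or stops it. Under Section 6.6 a stop also ends dose escalation.

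**Working it through.** **Platelet rule**

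The protocol gives no figure to reproduce here; the check is on the logic of the rules.

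Inputs: eligible counts 30–75 × 10⁹/L (Section 5.3); proceed criterion 5 and pause criterion 4 (Section 6.6). Let B be the pre-dose count and n the lowest post-dose count, in whole units of 10⁹/L.

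1. Criterion 5 fails when (B − n)/B > 0.30, that is n < 0.7B.
2. The platelet pause applies when n < 30 and n ≤ 0.7B, or when n ≤ 0.5B.
3. The gap (criterion 5 fails, no pause) is therefore n < 0.7B, n > 0.5B and n ≥ 30.
4. It is non-empty when 0.7B > 30, so B > 30/0.7 = 42.86. For whole counts that is B = 43 to 75. Below 43, any fall above 30% takes the count under 30 and the pause catches it.

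| B | 0.7B | 0.5B | Nadirs in the gap | Falls | Number of whole counts |
|---|---|---|---|---|---|
| 43 | 30.1 | 21.5 | 30 | 30.2% | 1 |
| 50 | 35.0 | 25.0 | 30–34 | 40.0% to 32.0% | 5 |
| 60 | 42.0 | 30.0 | 31–41 | 48.3% to 31.7% | 11 |
| 75 | 52.5 | 37.5 | 38–52 | 49.3% to 30.7% | 15 |

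Over all B, nadirs in the gap run from 30 to 52, within the eligible 30–75. These tallies count possible values. They are not probabilities, because the documents give no baseline distribution.

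Example: 75 to 45 is (75 − 45)/75 = 40.0%. Criterion 5 fails (45 < 52.5), but 45 is above both 30 and 37.5, so nothing pauses. With no AE reported, the first alternative is met and dosing may proceed. Add one unrelated mild headache and only the second alternative is open; criterion 5 then bars the next dose.

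If no AE is reported, criteria 1 and 2, which concern AEs, are met automatically. The first alternative therefore does no work except to release criteria 3, 4 and 5. The pause and stop lists stand on their own, so in practice what is lost is criterion 3 (clinically significant changes) and the 30% limit.

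Exposure: Section 2.3 places the platelet reduction in a healthy participant at 1 mg/kg IV, where Table 6 gives C_max 24.7 µg/mL. Table 7 gives observed SC values of 0.895, 1.37 and 2.64 µg/mL at 25, 50 and 100 mg. The ratios are 24.7/0.895 = 27.6, 24.7/1.37 = 18.0 and 24.7/2.64 = 9.4.

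**Hypotension and hypoxia**

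- Appendix 9 grades neither. The amendment history confirms that the two rows were taken out, on the ground that the CRS table covers these events.
- In that table (Appendix 10, Table 13) every grade requires a temperature of at least 38 °C, waived only once a patient with CRS has received antipyretics. An event afebrile from onset has no grade there.
- A moderate event then lacks a tabulated Grade 2 for pause criterion 1, while pause criterion 3 leaves out events already identified as pro-inflammatory.
- A severe related event is a pause under pause criterion 2, but a stop if it counts as a Grade 3 pro-inflammatory event under stop criterion 1.

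**The case against.** On platelets, the opening words of criterion 5 suggest a limit intended for all ITP participants, and sensible staff would probably apply it that way. The bypass also needs several things at once: no AE of any kind; an investigator who attributes a 30–50% post-dose fall to ITP and finds it no worse than expected, although Appendix 3 requires timing to be weighed and the investigator's brochure consulted; a nadir of 30 or more; and a 96-hour safety review that lets it through. Section 4.1 makes that review mandatory for every participant and allows it to be extended, and Section 6.6 leaves the decision to continue with the principal investigator. All of this stands and limits the likely harm. None of it ties the decision to the 30% figure the sponsor chose.

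A reader might infer that the platelet limit is void, or that any fall can pass. The documents do not support that: the pause criterion works without an AE, and Appendix 3 could equally lead the investigator to record the fall.

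A reader might also infer that afebrile hypotension or hypoxia could let dosing continue unsafely. That is not supported either. A recorded AE closes the first alternative, a clinically significant vital-sign change fails proceed criterion 3, and a related serious AE is a stop in its own right. Proceed criterion 1 already names CTCAE, and Appendix 10 gives management thresholds for both events. What remains is a broken reference.

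**Conclusion.** The platelet point holds as a drafting defect worth correcting. As written, a fall above 30% and below 50% with nadir 30 × 10⁹/L or more, from a pre-dose count of 43 to 75, can meet no proceed bar, pause or stop criterion. Only the safety review and investigator judgment then stand between it and the next dose. The scale is small: at most 12 ITP participants dosed one at a time, a separate pause for Grade 2 bleeding, and SC exposure well below the IV level at which platelets fell.

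This assumes a literal reading of the alternative, that the report of no AE refers to the participant just dosed, and that the pre-dose count lies in the eligible range. Section 6.6 does not say whether the condition is per participant or per cohort; at cohort level any earlier AE would close the bypass.

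The grading point is secondary. It affects pause versus stop, mainly for afebrile, non-serious events.

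It does not follow that every fall above 30% should be a pause. That would make the sponsor's platelet thresholds in pause criterion 4 redundant, which is a policy choice and not a correction.

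**What to change.** In Section 6.6, delete the no-AE alternative from the proceed rule, or state that criteria 4 and 5 apply to every ITP participant whether or not an AE is reported. Leave the thresholds in pause criterion 4 as they are.

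For hypotension and hypoxia, replace the Appendix 9 reference with CTCAE v4.03 grades in the proceed, pause and stop criteria, so that afebrile events have a grade. Keep Appendix 9 for vomiting and diarrhea.

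The cost is amendment wording, with no added participants, visits or tests. Some dosing that could now go ahead would be held, which may slow the ITP cohorts. A hold in the gap would not be a pause, so the subteam review set out for pauses would not be triggered automatically; one sentence should say who may release it.
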